6.2 DATA SHARING PLANS

6.2.1 Human Data Sharing Plan

What data will be shared?

I will share human data generated in this research for future research as follows:

- Coded, linked data in an NIH-funded or approved public repository.
- Coded, linked data in BTRIS (automatic for activities in the Clinical Center)
- Identified or coded, linked data with approved outside collaborators under appropriate agreements.

How and where will the data be shared?

Data will be shared through:

- An NIH-funded or approved public repository. Such as: clinical trial.gov
- BTRIS (automatic for activities in the Clinical Center)
- Approved outside collaborators under appropriate individual agreements.
- Publication and/or public presentations.

When will the data be shared?

- Before publication.
- At the time of publication or shortly thereafter.

6.2.2 Genomic Data Sharing Plan

NIH Genomic Data Sharing Policy will not apply for this protocol as no genetic/genomic testing is performed.

6.3 RESPONSE CRITERIA

6.3.1 Modified RANO Response Criteria

Response will be assessed by Modified RANO criteria and as such, the first imaging following completion of radiation will be considered the baseline for response assessment as per Ellingson et al. Neurotherapeutics 2017[[25](#)].

| Response | Modified RANO response Criteria |
|------------------------|--|
| Complete response (CR) | 
Requires all of the following:
 
1. Disappearance of all enhancing measurable and non-measurable disease sustained for at least 4 weeks.2. No new lesions.3. Patients must be off corticosteroids (or on physiologic replacement doses only).4. Stable or improved clinical assessments (i.e. neurological examinations). 
Note: Patients with non-measurable disease only cannot have achieve CR; the best response possible is SD
 |
| Partial Response (PR) | 
Requires all of the following:
 
1. $\geq 50\%$ decrease in sum of products of perpendicular diameters or $\geq 65\%$ decrease in total volume of all measurable enhancing lesions compared with baseline, sustained for at least 4 weeks. If the second scan exhibits PD with respect to the “preliminary PR” scan, then the response is not sustained, noted as pseudoresponse, PsR, and is now considered “preliminary PD” (note confirmed PD requires at least two sequential increases in tumor volume). If the second scan exhibits SD, PR, or CR, it is considered a durable PR and the patient should continue on therapy until confirmed PD is observed2. No new lesion.3. Steroid dose should be the same or lower compared with baseline scan.4. Stable or improved clinical assessments. |

| Response | Modified RANO response Criteria |
|--------------------------|--|
| Progressive Disease (PD) | 
1. At least two sequential scans separated by at ≥ 4 weeks both exhibiting $\geq 25\%$ increase in sum of products of perpendicular diameters or $\geq 40\%$ increase in total volume of enhancing lesions.2. In the case where the baseline or best response demonstrates no measurable enhancing disease (visible or not visible), then any new measurable ($>10\text{mm} \times 10\text{mm}$) enhancing lesions are considered PD after confirmed by a subsequent scan ≥ 4 weeks exhibiting $\geq 25\%$ increase in sum of products of perpendicular diameters or $\geq 40\%$ increase in total volume of enhancing lesions relative to the scan first illustrating new measurable disease.3. Clear clinical deterioration not attributable to other causes apart from tumor (e.g. seizures, medication adverse effects, therapy complications, stroke, infection) or attributable to changes in steroid dose.4. Failure to return for evaluation as a result of death or deteriorating condition. |
| Stable disease (SD) | 
1. Does not qualify for CR, PR, or PD as defined above. Note this also applies to patients that demonstrate PsR when the confirmation scan does not show PD or PsP when the confirmation scan does not show PR/CR.2. In the event that corticosteroid dose was increased (for new symptoms/signs) without confirmation of disease progression on neuroimaging, and subsequent follow-up imaging shows that the steroid increase was required because of disease progression, the last scan considered to show stable disease will be the scan obtained when the corticosteroid dose was equivalent to the baseline dose. |

6.4 TOXICITY CRITERIA

The following adverse event management guidelines are intended to ensure the safety of each patient while on the study. RTOG morbidity score will be used for radiation related toxicity

([Appendix B](#) and [Appendix C](#)). The descriptions and grading scales found in the revised NCI Common Terminology Criteria for Adverse Events (CTCAE) version 5.0 will be utilized for AE reporting. All appropriate treatment areas should have access to a copy of the CTCAE version 5.0. A copy of the CTCAE version 5.0 can be downloaded from the CTEP web site (http://ctep.cancer.gov/protocolDevelopment/electronic_applications/ctc.htm).

7 NIH REPORTING REQUIREMENTS/DATA SAFETY MONITORING PLAN

7.1 DEFINITIONS

Please refer to definitions provided in Policy 801: Reporting Research Events found at: <https://irbo.nih.gov/confluence/pages/viewpage.action?pageId=36241835#Policies&Guidance-800Series-ComplianceandResearchEventReportingRequirements>.

7.2 OHSRP OFFICE OF COMPLIANCE AND TRAINING / IRB REPORTING

7.2.1 Expedited Reporting

Please refer to the reporting requirements in Policy 801: Reporting Research Events and Policy 802 Non-Compliance Human Subjects Research found at:

<https://irbo.nih.gov/confluence/pages/viewpage.action?pageId=36241835#Policies&Guidance-800Series-ComplianceandResearchEventReportingRequirements>. Note: Only IND Safety Reports that meet the definition of an unanticipated problem or present new information that might affect the willingness of participants to enroll or remain on the study will need to be reported per these policies.

7.2.2 IRB Requirements for PI Reporting at Continuing Review

Please refer to the reporting requirements in Policy 801: Reporting Research Events found at: <https://irbo.nih.gov/confluence/pages/viewpage.action?pageId=36241835#Policies&Guidance-800Series-ComplianceandResearchEventReportingRequirements>.

7.3 NCI CLINICAL DIRECTOR REPORTING

Problems expeditiously reviewed by the OHSRP in the NIH eIRB system will also be reported to the NCI Clinical Director/designee; therefore, a separate submission for these reports is not necessary.

In addition to those reports, all deaths that occur within 30 days after receiving a research intervention should be reported via email unless they are due to progressive disease.

To report these deaths, please send an email describing the circumstances of the death to [contact] within one business day of learning of the death

7.4 NIH REQUIRED DATA AND SAFETY MONITORING PLAN

7.4.1 Principal Investigator/Research Team

The clinical research team will meet on a weekly basis when patients are being actively treated on the trial to discuss each patient. Decisions about dose level enrollment and dose escalation if applicable will be made based on the toxicity data from prior patients.

All data will be collected in a timely manner and reviewed by the principal investigator or a lead associate investigator. Events meeting requirements for expedited reporting as described in section [7.2.1](#) will be submitted within the appropriate timelines.

The principal investigator will review adverse event and response data on each patient to ensure safety and data accuracy. The principal investigator will personally conduct or supervise the investigation and provide appropriate delegation of responsibilities to other members of the research staff.

8 SPONSOR PROTOCOL/SAFETY REPORTING

8.1 DEFINITIONS

8.1.1 Adverse Event

Any untoward medical occurrence in a patient or clinical investigation subject administered a pharmaceutical product and which does not necessarily have a causal relationship with this treatment. An adverse event (AE) can therefore be any unfavorable and unintended sign (including an abnormal laboratory finding), symptom, or disease temporally associated with the use of a medicinal (investigational) product, whether or not related to the medicinal (investigational) product (ICH E6 (R2)).

8.1.2 Treatment-emergent adverse event (TEAE)

Any event that was not present prior to the initiation of study treatment or any event already present that worsens in either intensity or frequency following exposure to study treatment.

8.1.3 Serious Adverse Event (SAE)

An adverse event or suspected adverse reaction is considered serious if in the view of the investigator or the sponsor, it results in any of the following:

- Death,
- A life-threatening adverse event (see [8.1.4](#))
- Inpatient hospitalization or prolongation of existing hospitalization
 - A hospitalization/admission that is pre-planned (i.e., elective or scheduled surgery arranged prior to the start of the study), a planned hospitalization for pre-existing condition, or a procedure required by the protocol, without a serious deterioration in health, is not considered a serious adverse event.
 - A hospitalization/admission that is solely driven by non-medical reasons (e.g., hospitalization for patient or subject convenience) is not considered a serious adverse event.
 - Emergency room visits or stays in observation units that do not result in admission to the hospital would not be considered a serious adverse event. The reason for seeking medical care should be evaluated for meeting one of the other serious criteria.
- Persistent or significant incapacity or substantial disruption of the ability to conduct normal life functions
- A congenital anomaly/birth defect.

- Important medical events that may not result in death, be life-threatening, or require hospitalization may be considered a serious adverse drug experience when, based upon appropriate medical judgment, they may jeopardize the patient or subject and may require medical or surgical intervention to prevent one of the outcomes listed in this definition.

8.1.4 Life-threatening

An adverse event or suspected adverse reaction is considered "life-threatening" if, in the view of either the investigator or sponsor, its occurrence places the patient or subject at immediate risk of death. It does not include an adverse event or suspected adverse reaction that, had it occurred in a more severe form, might have caused death. (21CFR312.32).

8.1.5 Severity

The severity of each Adverse Event will be assessed utilizing the CTCAE version 5.0.

8.1.6 Relationship to Study Product

All AEs will have their relationship to study product assessed using the terms: related or not related.

- Related – There is a reasonable possibility that the study product caused the adverse event. Reasonable possibility means that there is evidence to suggest a causal relationship between the study product and the adverse event.
- Not Related – There is not a reasonable possibility that the administration of the study product caused the event.

8.2 ASSESSMENT OF SAFETY EVENTS

AE information collected will include event description, date of onset, assessment of severity and relationship to study product and alternate etiology (if not related to study product), date of resolution of the event, seriousness and outcome. The assessment of severity and relationship to the study product will be done only by those with the training and authority to make a diagnosis and listed on the Form FDA 1572 as the site principal investigator or sub-investigator. AEs occurring during the collection and reporting period will be documented appropriately regardless of relationship. AEs will be followed through resolution.

SAEs will be:

- Assessed for severity and relationship to study product and alternate etiology (if not related to study product) by a licensed study physician listed on the Form FDA 1572 as the site principal investigator or sub-investigator.
- Recorded on the appropriate SAE report form, the medical record and captured in the clinical database.
- Followed through resolution by a licensed study physician listed on the Form FDA 1572 as the site principal investigator or sub-investigator.

For timeframe of recording adverse events, please refer to section **6.1**. All serious adverse events recorded from the time of first investigational product administration must be reported to the sponsor with the exception of any listed in section **8.4**.

8.3 REPORTING OF SERIOUS ADVERSE EVENTS

Any AE that meets a protocol-defined serious criteria or meets the definition of Adverse Event of Special Interest that require expedited reporting must be submitted immediately (within 24 hours of awareness) to OSRO Safety using the CCR SAE report form. Any exceptions to the expedited reporting requirements are found in section **8.4**.

All SAE reporting must include the elements described in **8.2**.

SAE reports will be submitted to the Center for Cancer Research (CCR) at: [contact] and to the CCR PI and study coordinator. CCR SAE report form and instructions can be found at: <https://nih.sharepoint.com/:u/r/sites/NCI-CCR-OCD-Communications/SitePages/Forms-and-Instructions.aspx?csf=1&web=1&e=uWBXtI>

Following the assessment of the SAE by OSRO, other supporting documentation of the event may be requested by the OSRO Safety and should be provided as soon as possible.

8.4 WAIVER OF EXPEDITED REPORTING TO CCR

Progression of the malignancy disease (including fatal outcomes) should NOT be reported as an SAE during the study or within the safety reporting period. Any sudden or unexplained death should be reported as an SAE. If there is any uncertainty about a finding being due solely to progression of malignancy disease, the finding should be reported as an AE or SAE, as appropriate.

8.5 SAFETY REPORTING CRITERIA TO THE PHARMACEUTICAL COLLABORATORS

Reporting will be per the collaborative agreement.

8.6 REPORTING PREGNANCY

All required pregnancy reports/follow-up to OSRO will be submitted to: [contact] and to the CCR PI and study coordinator. Forms and instructions can be found here: <https://nih.sharepoint.com/:u/r/sites/NCI-CCR-OCD-Communications/SitePages/Forms-and-Instructions.aspx?csf=1&web=1&e=uWBXtI>

8.6.1 Maternal exposure

If a patient becomes pregnant during the course of the study, the study treatment should be discontinued immediately, and the pregnancy reported to the Sponsor no later than 24 hours of when the Investigator becomes aware of it. The Investigator should notify the Sponsor no later than 24 hours of when the outcome of the Pregnancy become known,

Pregnancy itself is not regarded as an SAE. However, congenital abnormalities or birth defects and spontaneous miscarriages that meet serious criteria (section **8.1.3**) should be reported as SAEs.

The outcome of all pregnancies should be followed up and documented.

8.6.2 Paternal exposure

Male patients should refrain from fathering a child or donating sperm during the study and for one month after the last dose of temozolomide.

Pregnancy of the patient's partner is not considered to be an AE. The outcome of all pregnancies occurring from the date of the first dose until one month after last dose of temozolomide should, if possible, be followed up and documented. Pregnant partners may be offered the opportunity to participate in an institutional pregnancy registry protocol (e.g., the NIH IRP pregnancy registry study) to provide data about the outcome of the pregnancy for safety reporting purposes.

8.7 REGULATORY REPORTING FOR STUDIES CONDUCTED UNDER CCR SPONSORED IND

Following notification from the investigator, CCR, the IND sponsor, will report any suspected adverse reaction that is both serious and unexpected. CCR will report an AE as a suspected adverse reaction only if there is evidence to suggest a causal relationship between the study product and the adverse event. CCR will notify FDA and all participating investigators (i.e., all investigators to whom the sponsor is providing drug under its INDs or under any investigator's IND) in an IND safety report of potential serious risks from clinical trials or any other source, as soon as possible, in accordance to 21 CFR Part 312.32.

All serious events will be reported to the FDA at least annually in a summary format.

8.8 SPONSOR DEVIATION REPORTING

A Protocol Deviation is defined as any non-compliance with the clinical trial Protocol, Manual of Operational Procedures (MOP) and other Sponsor approved study related documentsGCP, or protocol-specific procedural requirements on the part of the participant, the Investigator, or the study site staff inclusive of site personnel performing procedures or providing services in support of the clinical trial.

It is the responsibility of the study Staff to document any protocol deviation identified by the Staff or the site Monitor in the CCR Protocol Deviation Tracking System (PDTs) online application. The entries into the PDTs online application should be timely, complete, and maintained per CCR PDTs user requirements. In addition, any deviation to the protocol should be documented in the participant's source records and reported to the reviewing IRB per their guidelines. OSRO required protocol deviation reporting is consistent with E6(R2) GCP: Integrated Addendum to ICH E6(R1): 4.5 Compliance with Protocol; 5.18.3 (a), and 5.20 Noncompliance; and ICH E3 16.2.2 Protocol deviations.

9 CLINICAL MONITORING

Clinical site monitoring is conducted to ensure:

- that the rights of the participants are protected;
- that the study is implemented per the approved protocol, Good Clinical Practice and standard operating procedures; and,
- the quality and integrity of study data and data collection methods are maintained.

Monitoring for this study will be performed by NCI CCR Office of Sponsor and Regulatory Oversight (OSRO) and Regulatory Oversight Support (SROS) Services contractor. Clinical site monitoring activities will be based on OSRO standards, FDA Guidance E6(R2) Good Clinical Practice: Integrated Addendum to ICH E6(R1) March 2018, and applicable regulatory requirements.

Details of clinical site monitoring will be documented in a Clinical Monitoring Plan (CMP) developed by OSRO. CMPs will be protocol-specific, risk-based and tailored to address human subject protections and integrity of the study data. OSRO will determine the intensity and frequency of monitoring based on several factors, including study type, phase, risk, complexity, expected enrollment rate, and any unique attributes of the study and the site. The Sponsor will conduct a periodic review of the CMP to confirm the plan's continued appropriateness. A change to the protocol, significant or pervasive non-compliance with GCP, or the protocol may trigger CMP updates.

OSRO SROS Monitoring visits and related activities will be conducted throughout the life cycle of each protocol. The first activity is before the study starts to conduct a Site Assessment Visit (SAV) (as warranted), followed by a Site Initiation Visit (SIV), Interim Monitoring Visit(s) (IMVs), and a study Close-Out Visit (COV).

Some monitoring activities may be performed remotely, while others will occur at the study site(s). Monitoring visit reports will describe visit activities, observations, and associated action items or follow-up required for resolution of any issues, discrepancies, or deviations. Monitoring reports will be distributed to the study PI, NCI CCR QA, CCR Protocol Support Office, coordinating center (if applicable), and the Sponsor regulatory file.

The site Monitor will inform the study team of any deviations observed during monitoring visits. If unresolved, the Monitor will request that the site Staff enter the deviations in the CCR Protocol Deviation Tracking System (PDTs) for deviation reporting to the Sponsor and as applicable per institutional and IRB guidance.

10 STATISTICAL CONSIDERATIONS

10.1 STATISTICAL HYPOTHESIS

10.1.1 Primary Endpoint

Define the maximum tolerated dose (MTD) of Selinexor given concurrently with radiation and temozolomide. Assessment of toxicities for dose escalation will occur for 30 days following the completion of RT.

10.1.2 Secondary Endpoint

Define the dose-limiting toxicities including effects on QOL and neurocognition in the setting of the addition of Selinexor to concurrent radiation therapy and temozolomide.

10.2 SAMPLE SIZE DETERMINATION

The primary objective of this trial is to determine the safety, toxicity profile, DLT and maximum tolerated dose (MTD) of Selinexor given concurrently alongside temozolomide and radiation in patients with newly diagnosed glioblastoma patients. There are 3 planned dose levels for this trial that will enroll 1 to 6 patients each using the 3+3 design to define the MTD. The MTD will be based on the assessment of DLT within one month following the irradiation, and will be defined as the dose level at which less than one-third of patients (0/3 or 0-1/6 patients) treated at that dose level experience a DLT, with the next higher dose level demonstrating a one-third or greater number of patients ($\geq 2/3$ or $\geq 2/6$ patients) having DLT. If a patient did not experience DLT and did not finish therapy, he or she will not be evaluable for determination of the MTD

and will be replaced in the dose level. An additional 3 to 6 patients will be enrolled at the MTD, so that a total of 9 patients will be treated at this dose to better characterize the clinical activity of this combination in this patient population. Thus, if all 3 dose levels are evaluated (6 patients per dose level with 9 total patients at the MTD or maximum administered dose), a maximum of 21 evaluable patients will be enrolled. Similarly, if all dose levels are evaluated, the minimum number of evaluable patients required will be 15. To compensate for inevaluable patients, an additional 3 patients may be enrolled. Thus, a maximal of 24 patients are targeted for this study. It is expected that accrual can be completed in 24 months.

Using this dose escalation scheme, the probability of escalating to the next dose level, based on the true rate of DLT at the current dose, is given by the following table (each group will be considered independently of the other):

| True rate of DLT at a given dose | 10% | 20% | 30% | 40% | 50% | 60% |
|----------------------------------|-----|-----|-----|-----|-----|-----|
| Probability of escalating | .91 | .71 | .49 | .31 | .17 | .08 |

10.3 POPULATIONS FOR ANALYSES

10.3.1 Evaluable for toxicity

All patients will be evaluable for toxicity from the time of their first treatment with Selinexor.

10.3.2 Evaluable for response

Only those patients who have completed radiation treatment will be considered evaluable for response.

10.4 STATISTICAL ANALYSES

10.4.1 General Approach

This is a phase I single arm dose escalation study of Selinexor in combination of radiation and temozolomide for patients with newly diagnosed Glioblastoma. Cohorts of 3-6 patients are evaluated at each dose level. The dose level on which 2 patients experience unacceptable toxicity is considered to have exceeded the MTD. The next lower dose level on which no more than 1/6 patients experience unacceptable toxicity is considered the MTD for this study.

10.4.2 Analysis of the Primary Endpoints

The primary endpoint will be to define the MTD of this approach.

10.4.3 Analysis of the Secondary and Exploratory Endpoint(s)

- Define the dose-limiting toxicities of Selinexor in combination with external beam radiation therapy (RT) and temozolomide in patients with newly diagnosed with glioblastoma or gliosarcoma. DLT's will be reported descriptively.
- Determine progression-free survival and overall survival. Time to progression will be determined by the interval from initiation of treatment on protocol to progression as per RANO criteria or death due to disease progression. For patients without progression, time to progression will be censored at last assessment date per RANO criteria. Survival duration will be determined by the interval from initiation of

treatment on protocol to date of death due to any cause. For patients alive as of last follow-up, time to death will be censored at last contact date.

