3.1.5 Dose Escalation

This study will use a 3+3 design, with 3-6 patients enrolled per dose level to define maximum tolerated dose (MTD). The MTD is the dose level at which no more than 1 of up to 6 patients experience DLT within 1 month of completion of treatment, and the dose below that at which at least 2 (of ≤6) patients have DLT as a result of selinexor/RT/temozolomide. If a patient did not experience DLT and did not finish treatment, he or she will not be evaluable for toxicity and will be replaced in the dose level. Enrollment to a dose level would stop if 2 or more patients had a DLT.

The number of patients may be increased to 9 total patients at the MTD (provided no DLT) with a maximum of 21 evaluable patients enrolled and the minimum evaluable patients required will be 15. The once weekly dosing schedule was based on the results of the KCP-330-004 study Arm D. The twice weekly dose of 60mg is from KCP-330-004 Arm C.

| Dose Escalation Schedule of Selinexor | |
|--|--|
| Dose Level | |
| Level -1 | 80 mg on weeks 1, 4 |
| Level 1 | 80 mg on weeks 1, 2, 4, 5 |
| Level 2 | 60 mg twice a week on weeks 1, 2, 4, 5 |
| Level 3 | 60 mg twice a week, weeks 1-6 |

All patients will receive 2Gy daily RT plus 75mg/m² temozolomide.

Dose escalation will follow the rules outlined in the Table below.

| Number of Patients with DLT at a Given Dose Level | Escalation Decision Rule |
|---|--|
| 0 out of 3 | Enter up to 3 patients at the next dose level |
| ≥ 2 | Dose escalation will be stopped. This dose level will be declared the maximally administered dose (highest dose administered). Up to three (3) additional patients will be entered at the next lowest dose level if only 3 patients were treated previously at that dose. |
| 1 out of 3 | Enter up to 3 more patients at this dose level. 
• If 0 of these 3 patients experience DLT, proceed to the next dose level.• If 1 or more of this group suffer DLT, then dose escalation is stopped, and this dose is declared the maximally administered dose. Up to three (3) additional patients will be entered at the next lowest dose level if only 3 patients were treated previously at that dose. |
| ≤ 1 out of 6 at highest dose level below the maximally administered dose | This is the MTD and is generally the recommended phase 2 dose. At least 6 patients must be entered at the recommended phase 2 dose. |

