 - b. Serum chemistries: LDH, AST, ALT, alkaline phosphatases, bilirubin (total and direct), BUN, serum creatinine, serum electrolytes, glucose, calcium, magnesium, phosphorous, uric acid, albumin, amylase, lipase
- ⁷ QOL assessment will be performed at baseline, at completion of radiation and at all subsequent follow-up visits. The questionnaires are allowed to be completed within +/- 7 days from the scheduled dates.
- ⁸ May be completed by remote visit with a member of the study team (e.g., if the patient is not able to return to the NIH CC). A patient may be referred to their local provider or asked to come to the NIH CC for an in-person assessment, if clinically indicated, and at the discretion of the PI. In the case of any visits with participants' local providers, records will be obtained. Follow-up evaluations should occur at one month after the completion of therapy, followed by at least every 2-month intervals for the first 2 year(s), and then at least every 6 months thereafter for a total of 3 years following completion of radiation/ Temozolomide/ Selinexor.
- ⁹ Toxicity assessment, vital signs and weight measurement may be done weekly during the on treatment visit and as needed.
- ¹⁰ All follow-up appointments will take place within +/- 7 days of the designated timepoint.

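### Section 10.4.3 announces PFS but defines time to progression, so a death from another cause can be read either as an event or as censored

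*Combined protocol and SAP*

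**What the plan says.** Section 1.1.3 makes PFS and overall survival the exploratory objective, and 10.4.8 says both will be compared informally with historical outcomes. Section 10.4.3 holds the only definitions.

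- **Progression endpoint.** After naming PFS, 10.4.3 defines a time to progression, from initiation of protocol treatment "to progression as per RANO criteria or death due to disease progression".
- **Censoring.** "For patients without progression, time to progression will be censored at last assessment date per RANO criteria".
- **Overall survival, same bullet.** The interval runs from initiation of "treatment on protocol to date of death due to any cause".
- **RANO progression.** Section 6.3.1 lists as item 4 of progressive disease: "Failure to return for evaluation as a result of death or deteriorating condition". Item 3, clinical deterioration, is limited to deterioration attributable to the tumor. Item 4 has no such limit.
- **RANO baseline.** In 6.3.1, "the first imaging following completion of radiation will be considered the baseline for response assessment". The notes to the study calendar (3.5) add: "Follow-up evaluations should occur at one month after the completion of therapy". The calendar schedules no MRI during radiation.
- **Analysis sets.** Section 10.3.2 says: "Only those patients who have completed radiation treatment will be considered evaluable for response". For a patient who stops early without a DLT, 3.1.5 says "he or she will not be evaluable for toxicity and will be replaced in the dose level"; 10.2 makes the same provision for determining the MTD. No set is named for PFS.

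**The concern.** PFS ordinarily counts death from any cause, whereas time to progression does not. Section 10.4.3 uses the first label and supplies the second definition. Because overall survival in the same bullet counts any death, the restriction to progression deaths looks deliberate, yet the RANO limb of the same sentence brings in a criterion with no such restriction.

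The deaths whose status is unclear include possible toxic deaths: 14.1.2 lists sepsis, cardiac failure, multiple organ dysfunction and pulmonary embolism among selinexor's adverse effects. If those deaths are censored and the result is labelled PFS, the estimate is too high. The reader of the report could not tell which rule had been used, and the rule could be chosen after the deaths are known. Section 10.4.8 does not state how the historical outcomes define PFS, so the direction of any bias in that comparison cannot be determined either.

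**Working it through.** The documents state no PFS figure, so there is none to reproduce. The check is first textual, then a calculation of what one death can do.

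**1. The two readings.** Take a patient who dies of a cause other than progression, with no earlier progression.

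| Reading | Governing text | Status of the death |
|---|---|---|
| A | 6.3.1, item 4, through the RANO limb of 10.4.3 | Event |
| B | Cause restriction in 10.4.3 | Censored at last RANO assessment |

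Under A the separate limb for progression deaths adds nothing. Under B item 4 has to be narrowed without the text saying so. Neither reading gives full effect to both clauses.

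**2. Missing censoring date under B.** The first post-radiation scan is the RANO baseline. It falls at about 6 weeks of radiation plus one month: 6 + 30.4/7 = 10.3 weeks from the start. A non-progression death before then has no RANO assessment date at which to censor.

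**3. Who is analysed.** If all treated patients are included, the window without a date is the whole 10.3 weeks. If the response-evaluable set of 10.3.2 were used, deaths during radiation would drop out and the window would be only the month between the end of radiation and the first scan. The replacement rules in 3.1.5 and 10.2 concern toxicity and the MTD and do not settle this.

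**4. Effect of one early death, reading B against A.** Inputs are n = 15, 21 and 24 (minimum evaluable, maximum evaluable and accrual ceiling, 10.2). Assume no other censoring and censoring of the death at day 0. If k patients are progression-free at a later time t, the estimate is k/n under A and k/(n−1) under B, a ratio of n/(n−1). At an assumed true 50%, the shift is 0.5/(n−1) and the standard error is √(0.25/n).

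| n | Ratio n/(n−1) | Shift at 50% | Standard error |
|---|---|---|---|
| 15 | 15/14 = 1.071 | 0.5/14 = 3.6 points | 12.9 points |
| 21 | 21/20 = 1.050 | 0.5/20 = 2.5 points | 10.9 points |
| 24 | 24/23 = 1.043 | 0.5/23 = 2.2 points | 10.2 points |

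**5. More than one death.** Assume n = 21, 8 progressions by 6 months, d early non-progression deaths and no other censoring. The 6-month estimate is (21−8−d)/21 under A and (21−8−d)/(21−d) under B.

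- d = 1: 12/21 = 57.1% against 12/20 = 60.0%
- d = 2: 11/21 = 52.4% against 11/19 = 57.9%
- d = 3: 10/21 = 47.6% against 10/18 = 55.6%

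**6. Effect on the median, constant hazards.** If non-progression deaths are a share f of the first-event hazard, the median under B exceeds the median under A by 1/(1−f) − 1. For assumed f = 5%, 10% and 20% this is 5%, 11% and 25%. The shares are illustrative; the documents give none.

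**The case against.** The strongest reply is that the conflict is overstated. The endpoint sentence names progression deaths as a separate limb, and item 4 would make that limb redundant. A reader giving every word effect would restrict deaths by cause, leaving a mislabelled endpoint rather than an ambiguous one. This has force: reading B is the plainer one. It does not remove the problem, because under B non-progression deaths are censored and the result is reported as PFS. Reading A also remains open, since 6.3.1 is the only RANO table in the protocol.

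Second, 3.8.1 makes progression under 6.3.1 a reason to leave protocol therapy, clinical deterioration needs no scan, and weekly on-treatment visits are scheduled. A RANO judgement during radiation is therefore conceivable. That is so, but the protocol does not call those visits RANO assessments. The calculation in step 4 also gives the same ratio for any censoring date before the first progression.

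Third, the stakes are low. PFS is exploratory, has no test or power attached, and the historical comparison is informal. At an assumed 50%, the shift per death is only about 0.2 to 0.3 of a standard error, and the larger figures rest on assumed death counts or shares. All of this stands. It limits the importance of the point, not its correctness.

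Fourth, the analysis-set and historical-series points would be minor on their own, and no historical PFS series is named; the outcomes cited for newly diagnosed glioblastoma in 1.2.1 are survival figures. That also stands. They are included because the PFS definition is incomplete without them.

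**Conclusion.** The concern holds. Section 10.4.3 labels as PFS an endpoint whose only named deaths are those due to progression, while the criteria it cites count death without regard to cause. No other section defines PFS or says which rule prevails.

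The size is unknown, because it depends on how many non-progression deaths occur. It is zero if item 4 governs or if there are none. On the censored reading, a single early death raises later estimates by 4.3% to 7.1% in relative terms, which at an assumed 50% is 2.2 to 3.6 points and well inside the sampling error. This rests on no other censoring and on a censoring date before any progression. The consequence is confined to the reported PFS and its informal historical comparison. The MTD, dose escalation, sample size and overall survival are not affected.

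**What to change.** In 10.4.3:

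- Define PFS as the time from initiation of protocol treatment to progression under 6.3.1 (keeping the deteriorating-condition part of item 4) or death from any cause, whichever comes first.
- Censor only patients who are alive and progression-free, at their last RANO assessment, with a stated default such as day 0 if there is none.
- State that, for this analysis only, the any-cause rule supersedes the death part of item 4.
- Name the PFS analysis set. All patients who start protocol treatment would match the stated time origin.
- If time to progression is also wanted, report it separately under that name.

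In 10.4.8, state the PFS definition used by whichever historical series is chosen.

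The cost is three or four sentences in 10.4.3 and one in 10.4.8, once a comparator has been selected. No new data are needed, since the date of death from any cause is already required for overall survival. The one downside is that reported PFS may be slightly shorter. The change should be made before the analysis, so that the rule is not chosen with the deaths in view.
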